11.4 Measurement of Effect

11.41 Target Lesions & Target Lymph Nodes

- Measurable lesions (as defined in Section 11.21) up to a maximum of 5 lesions, representative of all involved organs, should be identified as “Target Lesions” and recorded and measured at baseline. These lesions

can be non-nodal or nodal (as defined in 11.21), where no more than 2 lesions are from the same organ and no more than 2 malignant nodal lesions are selected.

Note: If fewer than 5 target lesions and target lymph nodes are identified (as there often will be), there is no reason to perform additional studies beyond those specified in the protocol to discover new lesions.

- Target lesions and target lymph nodes should be selected on the basis of their size, be representative of all involved sites of disease, but in addition should be those that lend themselves to reproducible repeated measurements. It may be the case that, on occasion, the largest lesion (or malignant lymph node) does not lend itself to reproducible measurements in which circumstance the next largest lesion (or malignant lymph node) which can be measured reproducibly should be selected.
- Baseline Sum of Dimensions (BSD): A sum of the longest diameter for all target lesions plus the sum of the short axis of all the target lymph nodes will be calculated and reported as the baseline sum of dimensions (BSD). The BSD will be used as reference to further characterize any objective tumor response in the measurable dimension of the disease.
- Post-Baseline Sum of the Dimensions (PBSD): A sum of the longest diameter for all target lesions plus the sum of the short axis of all the target lymph nodes will be calculated and reported as the post-baseline sum of dimensions (PBSD). If the radiologist is able to provide an actual measure for the target lesion (or target lymph node), that should be recorded, even if it is below 0.5 cm. If the target lesion (or target lymph node) is believed to be present and is faintly seen but too small to measure, a default value of 0.5 cm should be assigned. If it is the opinion of the radiologist that the target lesion or target lymph node has likely disappeared, the measurement should be recorded as 0 cm.
- The minimum sum of the dimensions (MSD) is the minimum of the BSD and the PBSD.

11.42 Non-Target Lesions & Non-Target Lymph Nodes

Non-measurable sites of disease (Section 11.22) are classified as non- target lesions or non-target lymph nodes and should also be recorded at baseline. These lesions and lymph nodes should be followed in accord with 11.433.

11.43 Response Criteria

11.431 All target lesions and target lymph nodes followed by CT/MRI must be measured on re-evaluation at evaluation times specified in Section 11.1. Specifically, a change in objective status to either a PR or CR cannot be done without re-measuring target lesions and target lymph nodes.

Note: Non-target lesions and non-target lymph nodes should be evaluated at each assessment, especially in the case of first response or confirmation of response. In selected circumstances, certain non-target organs may be evaluated less frequently. For example, bone scans may need to be repeated only when complete response is identified in target disease or when progression in bone is suspected.

11.432 Evaluation of Target Lesions

- Complete Response (CR): All of the following must be true:
 - a. Disappearance of all target lesions.
 - b. Each target lymph node must have reduction in short axis to <1.0 cm.
- Partial Response (PR): At least a 30% decrease in PBS (sum of the longest diameter for all target lesions plus the sum of the short axis of all the target lymph nodes at current evaluation) taking as reference the PBS (see Section 11.41).
- Progression (PD): At least one of the following must be true:
 - a. At least one new malignant lesion, which also includes any lymph node that was normal at baseline (< 1.0 cm short axis) and increased to \geq 1.0 cm short axis during follow-up.
 - b. At least a 20% increase in PBS (sum of the longest diameter for all target lesions plus the sum of the short axis of all the target lymph nodes at current evaluation) taking as reference the MSD (Section 11.41). In addition, the PBS must also demonstrate an absolute increase of at least 0.5 cm from the MSD.
 - c. See Section 11.32 for details in regards to the requirements for PD via FDG-PET imaging.
- Stable Disease (SD): Neither sufficient shrinkage to qualify for PR, nor sufficient increase to qualify for PD taking as reference the MSD.

11.433 Evaluation of Non-Target Lesions & Non-target Lymph Nodes

- Complete Response (CR): All of the following must be true:
 - a. Disappearance of all non-target lesions.

- b. Each non-target lymph node must have a reduction in short axis to <1.0 cm.
- Non-CR/Non-PD: Persistence of one or more non-target lesions or non-target lymph nodes.
- Progression (PD): At least one of the following must be true:
 - a. At least one new malignant lesion, which also includes any lymph node that was normal at baseline (< 1.0 cm short axis) and increased to \geq 1.0 cm short axis during follow-up.
 - b. Unequivocal progression of existing non-target lesions and non-target lymph nodes. (NOTE: Unequivocal progression should not normally trump target lesion and target lymph node status. It must be representative of overall disease status change.)
 - c. See Section 11.32 for details in regards to the requirements for PD via FDG-PET imaging.

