16.52 Overall Response Rate (ORR)

Overall response rate is defined as the number of patients with a complete response (CR) or partial response (PR) (as defined by the RECIST 1.1) divided by the number of evaluable patients in each arm at 12 months post registration. ORR will be compared between the 2 treatment arms. Confidence intervals for the true success proportion will be calculated according to the approach of Clopper and Pearson.

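### The target-lesion partial response rule in 11.432 measures the current sum against itself, contradicting the baseline reference in 11.41

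*Combined protocol and SAP*

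**What the plan says.** Section 11.432 defines target-lesion PR as "At least a 30% decrease in PBS". It explains PBS as the sum of target-lesion diameters and nodal short axes when the patient is evaluated, and then names the reference: "taking as reference the PBS (see Section 11.41").

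The cited Section 11.41 defines three quantities, none of them called PBS:

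- BSD, the baseline sum: "The BSD will be used as reference to further characterize any objective tumor response in the measurable dimension of the disease".
- PBSD, the sum at a later evaluation: "reported as the post-baseline sum of dimensions (PBSD").
- MSD, the minimum: "The minimum sum of the dimensions (MSD) is the minimum of the BSD and the PBSD".

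The progression rule in 11.432 uses a separate reference: "lymph nodes at current evaluation) taking as reference the MSD (Section 11.41"). Stable disease (SD) also refers to the MSD.

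PR counts towards two secondary endpoints. For 16.52, "Overall response rate is defined as the number of patients with a complete response (CR) or partial response (PR"), divided by evaluable patients. The clinical benefit rate (CBR) in 16.53 adds stable disease of at least 6 months.

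**The concern.** A response rule needs two different quantities, a current sum and a reference sum. The PR line uses one term for both, and it cites a section that gives a different reference. It is the only target-lesion rule based on a percentage change or a reference sum that has this fault.

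At stake is the boundary between PR and SD, and so the objective response rate (ORR) and, to a lesser degree, CBR. Table 1 in Section 1.1 puts the response rate at 1.0% for regorafenib and 1.6% for TAS-102. Any misclassified responders would therefore be mainly in the panitumumab arm, which would bias the comparison of response against panitumumab.

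**Working it through.** No sample-size, power or alpha figure in the plan depends on this line, so there is no stated figure to reproduce. The check applies the rule under each possible reading.

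**Formula.** Percent decrease = (reference − current sum) / reference. Target-lesion PR requires at least 30% (11.432).

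**Reading 1: as printed, reference = current sum.** (PBS − PBS) / PBS = 0% for every non-zero sum. The threshold is never met.

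**Reading 2: reference = BSD, as 11.41 states.** The sums here are assumed for illustration. With a BSD of 10 cm:

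- current sum 6 cm: (10 − 6)/10 = 40%, PR met
- current sum 7 cm: (10 − 7)/10 = 30%, PR just met
- current sum 9 cm: (10 − 9)/10 = 10%, not PR

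**Reading 3: reference = a preceding post-baseline sum.** This does not rescue the rule.

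- The first restaging has no reference.
- BSD 10 cm, then 6 cm and 6 cm: the second evaluation shows (6 − 6)/6 = 0%, although the tumour is 40% below baseline.
- The opposite error is also possible. With a BSD of 10 cm, a patient who has not met the 20% progression rule can have a first post-baseline sum of just under 10 × 1.2 = 12 cm. A 30% fall from there is about 12 × 0.7 = 8.4 cm. That would score as PR although it is only (10 − 8.4)/10 = 16% below baseline.

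Readings 1 and 3 both conflict with 11.41. Only reading 2 agrees with it.

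**What reading 1 does to each endpoint.**

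- *ORR (16.52).* The 11.44 table still gives an overall status of PR when target lesions are CR and non-target lesions are Non-CR/Non-PD or not all evaluated. Every other PR would be lost.
- *CBR (16.53).* A patient who should be PR and has not progressed would be classed as SD. SD of at least 6 months still counts, so only responders with disease control under 6 months drop out.
- *Overall survival (OS, 16.11) and the decision rules (16.12 to 16.14).* These rest on deaths only, and nothing changes.
- *Progression-free survival (PFS, 16.51).* The target-lesion progression rule uses the MSD, and nothing changes.

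**The case against.** The strongest defence has four parts.

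1. **It may be a reading artefact.** PBS is defined nowhere, and it appears four times in 11.432, each time where a defined term ending in D would fit. The documents cannot settle this. BSD, PBSD and MSD were extracted correctly in 11.41, and MSD in 11.432, so an artefact is possible but not shown. The source PDF should be checked first.

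2. **The intent is plain.** The line points to 11.41, which names the BSD. Section 11.0, 16.52 and 16.53 point to RECIST 1.1. Most sites would probably measure from baseline. This stands as evidence of intent, but it does not correct the printed rule. Section 11 is the protocol's own text for evaluating response.

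3. **Little depends on the line.** OS is primary, secondary p-values are descriptive (16.5), and patients with CR, PR or SD all continue treatment (13.1). RECIST measurement forms are collected at baseline and at each evaluation (18.1), so response can be recomputed. All of this stands, and it limits the weight of the point.

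4. **Stronger readings go too far.** A reader might infer that ORR would consist of complete responses only. The 11.44 table does not support that, because overall PR remains reachable through target-lesion CR. A reader might also take the 38% response rate in Section 1.3 and conclude that 0.38 × 53 = about 20 panitumumab responders depend on this line. That rate comes from 13 patients selected by ddPCR for RAS and treated with irinotecan plus cetuximab. It does not come from panitumumab alone in patients selected by Guardant360. Taken as 5/13, its exact 95% interval is about 14% to 68%, or roughly 7 to 36 of 53. The figure also assumes that every site would apply a rule that always gives 0%. The documents support no firm count.

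**Conclusion.** The point holds as an internal contradiction in an operative definition. As printed, target-lesion PR cannot be met, and the rule conflicts with the section it cites. If applied literally, ORR would be understated, mainly in the panitumumab arm, and CBR would be understated to a smaller extent. The amount cannot be estimated from the documents, because no response rate is given for this regimen in this population and it is unknown whether any site would follow the literal text.

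The effect is confined to these secondary endpoints. It is also recoverable at analysis, provided the baseline and follow-up measurements are recorded as Section 18.1 plans. The conclusion assumes that the extracted text matches the source PDF and that PBS stands for the post-baseline sum, which its explanation in 11.432 and the definitions in 11.41 both suggest.

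**What to change.** Check the source PDF. If the PR line already names the BSD there, that line needs no change. If it reads as extracted:

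- name the BSD as the reference for PR in 11.432, to match 11.41;
- replace PBS with the defined term PBSD wherever it stands for the current sum in 11.432.

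If any responses have already been scored, recompute target-lesion response from the recorded sums against the BSD before ORR and CBR are analysed. The cost is a short textual correction. It needs no new data and no change to sample size, event count or decision rules.

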11.44 Overall Objective Status

The overall objective status for an evaluation is determined by combining the patient's status on target lesions, target lymph nodes, non-target lesions, non-target lymph nodes, and new disease as defined in the following tables:

For Patients with Measurable Disease

Target Lesions & Target Lymph Nodes	Non-Target Lesions & Non-Target Lymph Nodes	New Sites of Disease	Overall Objective Status
CR	CR	No	CR
CR	Non-CR/Non-PD	No	PR
PR	CR Non-CR/Non-PD	No	PR
CR/PR	Not All Evaluated*	No	PR**
SD	CR Non-CR/Non-PD Not All Evaluated*	No	SD
Not all Evaluated	CR Non-CR/Non-PD Not All Evaluated*	No	Not Evaluated (NE)
PD	Unequivocal PD CR Non-CR/Non-PD Not All Evaluated*	Yes or No	PD
CR/PR/SD/PD/Not all Evaluated	Unequivocal PD	Yes or No	PD

Target Lesions & Target Lymph Nodes	Non-Target Lesions & Non-Target Lymph Nodes	New Sites of Disease	Overall Objective Status
CR/PR/SD/PD/Not all Evaluated	CR Non-CR/Non-PD Not All Evaluated*	Yes	PD

*See Section 11.431

** NOTE: This study uses the protocol RECIST v1.1 template dated 2/16/2011. For data collection and analysis purposes the objective status changed from SD to PR in the ACCRU protocol RECIST v1.1 template as of 2/16/2011 and to match RECIST v1.1 requirements.

12.0 Descriptive Factors

- 12.1 ECOG PS: 0 vs. 1 vs. 2.
- 12.2 Disease characteristics: Unresectable vs. Metastatic.
- 12.3 Prior treatment: TAS-102 vs. regorafenib vs. neither.
- 12.4 Primary tumor location: cecum vs. ascending vs. hepatic flexure vs. transverse vs. splenic flexure vs. descending vs. sigmoid vs. rectosigmoid vs. rectum vs other.
- 12.5 Microsatellite instability or mismatch repair deficiency tested: Yes vs. no.
 - 12.5.1 If yes, MSI-High (MSI-H) vs. microsatellite stable/MSI-Low (MSS/MSI-L); loss of mismatch repair protein (MMR deficient, dMMR) vs. mismatch repair proteins intact (MMR proficient, pMMR).
- 12.6 *ERBB2* (HER2) amplification tested: Yes vs. no.
 - 12.6.1 If yes, *ERBB2* amplified vs. *ERBB2* equivocal vs. *ERBB2* not amplified.

13.0 Treatment/Follow-up Decision at Evaluation of Patient

- 13.1 Patients who have CR, PR, or SD will continue treatment per protocol for a maximum of 24 cycles. Subsequent treatment is at the discretion of their attending physician.
- 13.2 Patients who develop PD while receiving therapy or choose an alternative therapy will go to the event-monitoring phase and be followed for survival (i.e. event-monitoring phase) every 3 months (± 7 days) for 3 years after randomization (per Section 18.0). Subsequent treatment is at the discretion of their attending physician.
- 13.3 Patients who go off protocol treatment for any reason will go to the event-monitoring phase and be followed for survival (i.e. event monitoring phase) every 3 months (± 7 days) for 3 years after randomization (per Section 18.0). Subsequent treatment is at the discretion of their attending physician.
- 13.4 A patient is deemed *ineligible* if after registration, it is determined that at the time of registration, the patient did not satisfy each and every eligibility criteria for study entry. The patient may continue treatment off-protocol at the discretion of the

physician as long as there are no safety concerns, and the patient was properly registered. The patient will go directly to the event-monitoring phase of the study (or off study, if applicable).

- If the patient received treatment, all data up until the point of confirmation of ineligibility must be submitted. Event monitoring will be required per Section 18.0 of the protocol.
- If the patient never received treatment, on-study material must be submitted. The patient will not be followed for survival.

13.5 A patient is deemed a *major violation*, if protocol requirements regarding treatment in cycle 1 of the initial therapy are severely violated that evaluability for primary end point is questionable. All data up until the point of confirmation of a major violation must be submitted. The patient will go directly to the event-monitoring phase of the study. The patient may continue treatment off-protocol at the discretion of the physician as long as there are no safety concerns, and the patient was properly registered. Event monitoring will be required per Section 18.0 of the protocol.

13.6 A patient is deemed a *cancel* if he/she is removed from the study for any reason before any study treatment is given. On-study material and the Off Treatment Form must be submitted. The patient will not be followed for survival.

13.7 Patients have the option to complete cfDNA testing at study completion and are encouraged to re-register with protocol ACCRU-GI-1611 (COLOMATE). The results of the cfDNA test will be used in protocol ACCRU-GI-1611 (COLOMATE) to identify genomic alterations and facilitate enrollment on COLOMATE companion clinical trials. Sites will access results by creating an account at [REDACTED] Sites will be notified by Guardant Health via email when results are available in the portal. See detailed instructions on the ACCRU website under Manuals and Forms.

14.0 Body Fluid Biospecimens

14.1 Summary Table of Research Blood/Blood Products to Be Collected for This Protocol

Indicate if specimen is mandatory or optional	Collection tube description and/or additive (color of tube top)	Volume to collect per tube (number of tubes to be collected)	Blood product being processed and submitted by participating site	Baseline ¹	Prior to dosing on Day 1 of Cycle 2	Restaging ²	End of Treatment ³	Additional processing required at site after blood draw?	Storage /shipping conditions ⁴
Mandatory	EDTA K2 (Purple)	10 mL (1)	Whole Blood	X				No	Freeze /dry ice
Mandatory	EDTA K2 (Purple)	10 mL (4)	Platelet Poor Plasma and	X	X	X	X	Yes	Freeze /dry ice

			White blood cells					
Optional	Streck tube ⁵	10 mL (2)	Whole blood			X	No	Room temperature

1. May occur prior to treatment on Cycle 1 Day 1.
2. At time of radiographic assessments (i.e., every other cycle beginning on cycle 3) which may occur \leq 14 days prior to day 1 of new cycle (estimated 4 restagings per patient).
3. Discontinuation of study treatment.
4. After all samples have been processed according to kit instructions, ship all specimens according to shipping instructions (see Section 14.3 for detailed shipping instructions.) Patients have the option to complete cfDNA testing at study completion and are encouraged to re-register with protocol ACCRU-GI-1611. See section 13.7.

14.2 Kits are required for this study.

NOTE: You will be ordering and receiving kits from two different locations.

14.21 EDTA K2

- 14.211 Each kit will contain supplies and instructions for collecting, processing, and shipping specimens.
- 14.212 Participating institutions may obtain kits for **EDTA K2** by completing and faxing the Supply Order Form (found in the Forms Packet) to the number listed on the form. Fill out the site address to where the kits will be shipped on the Fax Supply form. A small but sufficient supply of the specimen collection kits should be ordered prior to patient entry. Unused/expired kits should be disposed of per institution policy. Do not send unused kits back to BAP.
Supply Order Forms must be filled in completely and legibly for quick processing.
- 14.213 Kits will be sent via FedEx Ground at no cost to the participating institutions. **Allow up to two weeks to receive the kits.**
- 14.214 Kits will not be sent via rush delivery service unless the participating institution provides their own FedEx account number or for express service. **ACCRU will not cover the cost for rush delivery of kits.**

14.22 Guardant 360 (Streck Tube)

- 14.221 In order to receive kits and access to the Guardant portal, fill out the Guardant Site Setup form for each treating location and email to [REDACTED]

- 14.222 Sites will create an account at [REDACTED] Once account is created, Guardant Health will ship the sites their kits and their own pre-printed Test Requisition Form(TRFs). Once that happens, kits and TRFs can be refreshed/replaced by contacting Guardant Health Client Services Team at [REDACTED] or [REDACTED]

14.3 Shipping and Handling

NOTE: You will be shipping kits to two different locations.

14.31 EDTA K2

- 14.311 Verify ALL sections of the Blood Specimen Submission Form (see Forms Packet), BAP Requisition Form (provided in kit) and specimen collection labels are completed and filled in correctly. Tube labels MUST match requisition form.
- 14.312 Specimens must be shipped the same day they are drawn.
- 14.313 Ship the EDTA tube in a combo shipper with the EDTA going into the side with a properly prepared cold pack. Place the frozen aliquots in the side for dry ice. Completely fill the box with dry ice pellets and be sure to label the weight of the dry ice on the shipping label. See kit instructions for specific details.
- 14.314 Ship specimens via Priority Overnight service, Monday – Friday, to BAP Freezer according to kit instructions. Do not send samples on weekends or just prior to federal holidays.
- 14.315 The BAP kits will include a smart shipper label (3x5 white barcoded label) affixed to the shipping boxes. The smart shipper label is a pre-addressed return label, which replaces the need for an air bill. Shipping costs will be covered by ACCRU if the shipping box provided with the BAP kit is used for shipping specimens to BAP Freezer.
- 14.316 BAP Freezer will receive the samples and immediately forward specimens to the ACCRU Research Base BAP Shared Resource, [name]. At study completion, specimens will be forwarded to the Duke Phase I Biomarker Laboratory located at Duke University for future processing.

14.32 Guardant 360 (Streck Tube)

- 14.321 Complete the Test Requisition Form and barcode labels (provided in kit).
- 14.322 Ship tubes the same day as collection with properly prepared gel pack. Do not freeze gel packs. Use as is.
- 14.323 Place the kit into the preprinted FedEx Clinical Pak and call FedEx for a pickup to be shipped to Guardant Health.
- 14.324 Detailed Blood Draw and Shipping Instructions are located on the ACCRU website under Manuals and Forms.

14.4 Study Methodology and Storage Information

- 14.41 Blood/blood product samples will be collected for the following research

14.411 Whole blood for pharmacogenomics

Whole blood will be stored for future pharmacogenetic assays (e.g., genetic polymorphisms such as those known to regulate angiogenesis, inflammation, immunity, auto-immunity, and antibody or drug action of clearance) that may correlate with efficacy and tolerability. The Duke Phase I Biomarker Laboratory located at Duke University may analyze the DNA for the presence of markers of interest using standard laboratory protocols.

14.412 Soluble protein (blood-based) biomarkers

Blood (platelet poor plasma, and white blood cells (buffy coat)) will be collected at baseline, every restaging, and progression for future analysis. The Duke Phase I Biomarker Laboratory located at Duke University may analyze for the following, but are not limited to soluble HGF, c-MET, EGF, HBEGF, HER1-3, FGFa, FGFb, VEGFA-D, PIGF, VEGFR2, GAS6, AXL, SDF1, Ang2, and TIE-2. Additional biomarkers may also be explored using multiplex array technology. Final biomarker selection will reflect the best science at the time of analysis.

14.413 Plasma for mutational analysis

Blood (platelet poor plasma) will be stored for future analysis of cell free DNA (cfDNA) and will be collected at baseline, every restaging, and at the 30-day post-treatment visit. The Duke Phase I Biomarker Laboratory located at Duke University may analyze for the following, but are not limited to *HER2* amplification, *EGFR* amplification, *BRAF* mutations, and extended KRAS/NRAS testing (exons 2, 3, and 4). Final biomarker selection will reflect the best science at the time of analysis.

14.414 Future use of patient samples

Any remaining biological materials (platelet poor plasma, and buffy coats) at the end of the study will be retained for possible use in future biomarker research.

